9.2. Measurements of Treatment Compliance

Any subjects who are enrolled but not vaccinated will be presented by treatment group as part of the subject disposition table ([Table 10](#).) Dates of treatment administration by treatment arm are presented in [Table 12](#).)

9.3. Adverse Events

When calculating the incidence of adverse events (i.e., on a per subject basis), each subject will only be counted once and any repetitions of adverse events within a subject will be ignored; the denominator will be

the total number of subjects in the safety population. All adverse events reported will be included in the summaries and analyses.

An overall summary of adverse events is presented in [Table 34](#). Unsolicited adverse events occurring in more than 5% of subjects in any treatment group are presented in [Table 35](#).

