5.3.5 Subject Replacement

Subjects who withdraw, are withdrawn/terminated from this study, or are lost to follow-up after signing the informed consent form and randomization but before receipt of study vaccine may be replaced. Subjects who are vaccinated, but do not complete the Day 15 visit, will be replaced. Subjects who are vaccinated and subsequently, after the Day 15 visit, withdraw, are withdrawn or terminated from this study, or are lost to follow-up will not be replaced. Subjects who were previously screened and found to be ineligible due to initial serum concentrations of PRN IgG \geq 20 IU/ml in protocol version 3.0 may be rescreened per the revised exclusion criterion of protocol version 4.0.

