At the screening visit, a physical examination will be performed by a study clinician licensed to make medical diagnoses and listed on the Form FDA 1572 as the site principal investigator or sub-investigator. On Visit 1, prior to study vaccination, and on Visits 2 and 3, a limited physical examination will be performed, focused on the nasopharynx, oropharynx, and lungs; in addition, a targeted physical examination will be performed, if indicated, based on review of interim medical history, by a study clinician. At follow-up visits 4, 4a and 5, a targeted physical examination may be performed, if indicated based on subject's interim medical history, by a study clinician.

Vital signs (oral temperature, pulse, and blood pressure) will be collected at the screening visit and prior to study vaccination. Vital signs assessed on Day 1 prior to vaccination will be considered as baseline. Subjects must not eat or drink anything hot or cold, or smoke within 10 minutes prior to taking oral temperature.

Reactogenicity assessments will include an assessment of solicited adverse events occurring from the time of each study vaccination through 14 days after study vaccination, which includes an assessment of mucosal reactions that include: runny nose, stuffy nose/congestion, nasal pain/irritation, epistaxis, sneezing, sinus pressure/pain, sore throat, cough, and shortness of breath, as well as systemic reactions that include fever, chills, fatigue, malaise, myalgia, arthralgia, headache, and hypersensitivity. Pre-administration reactogenicity assessments will be performed prior to study vaccination to establish baseline, then the study vaccination will be given.

Subjects will be observed in the clinic for approximately 2 hours after study vaccination. Post-administration reactogenicity assessments will be performed, and any AE/SAEs will be recorded on the appropriate data collection form prior to discharge from the clinic.

All subjects will complete a subject memory aid from the time of study vaccination through 14 days after study vaccination. Subject memory aids will be reviewed with the subjects for adverse events (solicited injection site and systemic reactions and unsolicited AEs) at follow-up visits occurring through approximately 14 days after study vaccination.

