3.2. Endpoints

3.2.1. Primary Outcome Measures

- Occurrence of solicited local and systemic reactogenicity from the time of the study vaccination through 14 days post-vaccination
- Occurrence of unsolicited non-serious adverse events from the time of the study vaccination through 28 days post-vaccination
- Occurrence of serious adverse events (SAEs) and new onset chronic medical conditions (NOCMCs) from the time of the study vaccination through approximately Day 181 post vaccination
- Occurrence of adverse events of special interest through approximately Day 29 post vaccination

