6. GENERAL STATISTICAL CONSIDERATIONS

6.1. General Principles

Unless otherwise noted, all continuous variables will be summarized using the following descriptive statistics: n (non-missing sample size), mean, standard deviation, median, maximum and minimum. The frequency and percentages (based on the non-missing sample size) of observed levels will be reported for all categorical measures. In general, all data will be listed, sorted by treatment group and subject, and when appropriate by visit number within subject. All summary tables will be structured with a column for each treatment in the order (BPZE1 10⁷ CFU administered via VaxINator, BPZE1 10⁹ CFU administered via VaxINator, BPZE1 10⁹ CFU administered via needleless tuberculin syringe, placebo administered via VaxINator) and will be annotated with the total population size relevant to that table/treatment, including any missing observations.

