6.3.1. Safety Population

The Safety Population will consist of all subjects who have received the study vaccine and for whom any data on safety are available. Subjects will be classified according to the treatment received. The primary safety analysis will be done on this population.

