14.3.1.1 Solicited Adverse Events

Table 36: Number and Percentage of Subjects Experiencing Solicited Events with 95% Confidence Intervals by Symptom and Treatment Group*

Symptom	BPZE1 10 ⁷ CFU by VaxINator (N=X)			BPZE1 10 ⁹ CFU by VaxINator (N=X)			BPZE1 10 ⁹ CFU by Syringe (N=X)			Placebo by VaxINator (N=X)			All Subjects (N=X)		
	n	%	95% CI	n	%	95% CI	n	%	95% CI	n	%	95% CI	n	%	95% CI
Any Symptom	x	xx	x x, x x	x	xx	x.x, x x	x	xx	x x, x.x	x	xx	x x, x.x	x	xx	x x, x.x
Any Systemic Symptom															
Fever															
Feverishness															
Fatigue (tiredness)															
Malaise (general unwell feeling)															
Myalgia (body aches /muscular pain)															
Arthralgia (joint pain)															
Headache															
Rash / hypersensitivity															
Any Local Symptom															
Runny nose															
Stuffy nose/congestion															
Nasal pain/ Irritation															
Epistaxis															
Sneezing															
Sinus pressure/pain															
Sore/irritated throat															
Cough															
Shortness of breath/wheezing															

Note: N= Number of subjects in the Safety Population

Table 37: Comparison of the Proportion of Subjects Experiencing Solicited Events by Treatment Group*

Symptom	Statistic	BPZE1 10 ⁷ CFU by VaxINator (N=X)	BPZE1 10 ⁹ CFU by VaxINator (N=X)	BPZE1 10 ⁹ CFU by Syringe (N=X)	Placebo by VaxINator (N=X)
Any Symptom	Proportion	x.xx	x.xx	x.xx	x xx
	95% CI (for proportion)	x xx, x.xx	x xx, x.xx	x xx, x.xx	x xx, x xx
	Difference ^a	x.xx	x.xx	N/A	N/A
	95% CI (for difference)	x xx, x.xx	x xx, x.xx	N/A	N/A
[Symptom 1]	Proportion	x.xx	x.xx	x.xx	x xx
	95% CI (for proportion)	x xx, x.xx	x xx, x.xx	x xx, x.xx	x xx, x xx
	Difference ^a	x.xx	x.xx	N/A	N/A
	95% CI (for difference)	x xx, x.xx	x xx, x.xx	N/A	N/A
Note: N = Number of subjects in the Safety Population who received at least one dose ^a vs. placebo					

Table 38: Number and Percentage of Subjects Experiencing Solicited Events by Symptom, Maximum Severity, and Treatment Group*

Symptom	Severity	BPZE1 10 ⁷ CFU by VaxINator (N=X)			BPZE1 10 ⁹ CFU by VaxINator (N=X)			BPZE1 10 ⁹ CFU by Syringe (N=X)			Placebo by VaxINator (N=X)			All Subjects (N=X)		
		n	%	95% CI	n	%	95% CI	n	%	95% CI	n	%	95% CI	n	%	95% CI
Any Symptom	None	x	xx	x.x, x x	x	xx	x x, x.x	x	xx	x.x, x x	x	xx	x x, x.x	x	xx	x x, x.x
	Mild															
	Moderate															
	Severe															
Systemic Symptoms																

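### Solicited-event rates in SAP Tables 36-39 use the whole Safety Population as denominator, so subjects with no solicited assessment after the 2-hour clinic check pull the rate for the first primary outcome downward

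*SAP*

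**What the plan says.** The first primary outcome is "Occurrence of solicited local and systemic reactogenicity from the time of the study vaccination through 14 days post-vaccination" (SAP 3.2.1).

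- **Denominator.** SAP 9.3, the parent of 9.3.1 on solicited events, counts each subject once and divides by "the total number of subjects in the safety population".
- **Who is in it.** SAP 6.3.1 admits "all subjects who have received the study vaccine and for whom any data on safety are available". No memory-aid data are required.
- **Table notes.** Table 36 carries "Note: N= Number of subjects in the Safety Population". Table 37, which gives the difference from placebo, uses "Number of subjects in the Safety Population who received at least one dose". Tables 38 and 39 also refer to the Safety Population. None of the four has a row for missing data.
- **By-day tables.** Tables 40-49 have a Not Reported row for every symptom.
- **General rules.** SAP 6.1 says, unless otherwise noted, "The frequency and percentages (based on the non-missing sample size) of observed levels will be reported for all categorical measures". SAP 9 allows either the non-missing number or the population as denominator and leaves the choice to be described table by table. SAP 6.5 rules out imputation.
- **Data collection.** Protocol 8.1 says "All subjects will complete a subject memory aid from the time of study vaccination through 14 days after study vaccination". Protocol 7.2 adds a 2-hour clinic observation after dosing.
- **Replacement.** Protocol 5.3.5: "Subjects who are vaccinated, but do not complete the Day 15 visit, will be replaced".

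**The concern.** The 2-hour check is enough to place a vaccinated subject in the Safety Population. If nothing solicited is recorded afterwards, the subject contributes almost nothing to a 14-day outcome but still adds one to the denominator. Dividing by the full population then has the same numerical effect as recording no reaction, although SAP 6.5 says missing values are not imputed.

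The protocol foresees subjects who could fall into this position. Those vaccinated without a Day 15 visit are replaced, but nothing removes them from the Safety Population, so replacement can enlarge N with partly observed subjects.

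Tables 36-38 are marked for the Preliminary Report, which may be shared for planning later trials (SAP 2.1), and Protocol 11.4 says the results will inform the Phase 2b dose. Table 37 sets the two VaxINator vaccine arms against placebo, so unequal loss would also shift the contrast.

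**Working it through.** **1. The plan's own figure.** The one stated safety figure that depends on the number observed per arm is in SAP Table 3: 79.4% for seeing at least one event of 10% frequency in 15 subjects. The formula 1 - (1 - p)^n gives 1 - 0.9^15 = 79.4%, so it reproduces. If m of the 15 are not observed, n becomes 15 - m, and the chance falls to 77.1%, 74.6% and 71.8% at m = 1, 2 and 3.

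**2. The same subject in different tables.** Take a subject with a clean 2-hour check and no later solicited assessment.

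| Place | Treatment of this subject |
|---|---|
| SAP 9.3; Tables 36-37 | In the denominator, not in the numerator |
| Tables 38-39 | In N, with no missing category; the SAP does not say whether to enter None or leave the subject out of the rows |
| Tables 40-49 | A Not Reported row is available for the unobserved days |
| SAP 6.1 default | Excluded from the percentage as missing |

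SAP 6.1 yields where another rule is noted, and 9.3 is such a rule. SAP 9 refers the reader to each table, and the only population named in the notes to Tables 36-39 is the Safety Population. The most specific text therefore gives the full denominator.

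**3. Size.** Inputs: N = 15 per VaxINator arm and 5 in the syringe arm (Protocol 5.3.1). The number m is assumed, because the documents give no loss rate. I also assume that loss is unrelated to reacting and that the m subjects had no reaction in the 2-hour check; if some did, the shortfall is smaller.

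Expected reported rate = p × (N - m)/N. Relative shortfall = m/N.

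| N | m | m/N | True 30% shown as | True 50% shown as | True 80% shown as |
|---|---|---|---|---|---|
| 15 | 0 | 0 | 30.0% | 50.0% | 80.0% |
| 15 | 1 | 7% | 28.0% | 46.7% | 74.7% |
| 15 | 2 | 13% | 26.0% | 43.3% | 69.3% |
| 5 | 1 | 20% | 24.0% | 40.0% | 64.0% |

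If the lost subjects are replaced, N grows with them, and m/N is at most 1/16 = 6%, 2/17 = 12%, or 1/6 = 17% in the syringe arm. These are upper limits, since a replaced subject may have attended Day 8.

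**4. Interval.** Exact 95% intervals with 7 reporters in an arm of 15:

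- Safety Population: 7/15 = 46.7% (21.3 to 73.4), width 52.1 points.
- m = 1: 7/14 = 50.0% (23.0 to 77.0), width 54.0 points.
- m = 2: 7/13 = 53.8% (25.1 to 80.8), width 55.7 points.

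The full-population interval sits lower and is narrower by about 2 to 4 points.

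**5. Difference from placebo.** Suppose the true rate is 60% in both arms, with 2 of 15 lost in one arm only. That arm shows 60% × 13/15 = 52%. The difference is -8 points if the loss is in the vaccine arm, +8 if it is in placebo, and zero if both lose the same share.

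**The case against.** A reader might infer that every unreturned memory aid is scored as 14 reaction-free days. The documents do not support that. No text scores a missing diary as None, SAP 6.5 rules out imputation, and the by-day tables can show the gap.

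Nor is the memory aid the only source after the clinic observation. The Day 8 and Day 15 visits include history, adverse-event recording and a focused examination. Early-termination and unscheduled visits within 15 days carry their own reactogenicity assessment (Protocol 7.3.1, 7.3.2, 7.5, 7.6). Listings 10 and 11 separate memory-aid from clinic data. The affected group is therefore only those with nothing solicited after the 2-hour check, which is smaller than all who miss Day 15.

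It can also be argued that the table notes only define the header N. SAP 6.1 says tables are annotated with the total population size, including missing observations, while percentages use non-missing data. This is fair as far as the notes go, and it shows that the wording is unreconciled. It does not answer SAP 9.3, which specifies the denominator itself.

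Finally, Table 10 shows by arm how many completed the Day 15 reactogenicity period, so a careful reader could detect loss. The plan expects few missing data, tests no formal hypothesis, and its intervals are wide in any case. All of that limits the likely size. It does not make the rates in Tables 36-37 correct when data are missing.

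**Conclusion.** The point holds as a conditional bias. SAP 9.3 and the notes to Tables 36-39 put under the first primary outcome a denominator that includes subjects not observed after the 2-hour check. The expected rate is multiplied by (N - m)/N: no effect at m = 0, a relative shortfall of 7% or 13% if 1 or 2 of 15 are affected, and 20% if 1 of 5 is affected. Each m is an assumption.

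It would go too far to say that the reported rates will be understated, or that the error favours the vaccine. The first requires actual loss; the second requires more loss in the vaccine arm than in placebo. What is established is a stated rule that lowers the rate whenever such subjects exist, in conflict with the SAP's general default and with its own by-day tables.

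**What to change.** - In SAP 9.3.1 and the notes to Tables 36-39, define the denominator as subjects with at least one solicited assessment, by memory aid or visit, after the 2-hour clinic observation, whether or not an event was reported. Entry must not depend on having reported a reaction, because that would push rates upward. Any post-dose assessment would be too loose a criterion, since the 2-hour check already meets it.
- Add to Tables 36-39 the Not Reported row already used in Tables 40-49.
- Show by arm the number with complete 14-day data, because one later assessment does not amount to full observation.
- Report the Safety Population rate as a sensitivity analysis. It keeps any 2-hour reactions in subjects without later data.
- Reconcile SAP 6.1, 9 and 9.3 so that one rule governs solicited events. Keep the Safety Population denominator for unsolicited adverse events and SAEs.

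The cost is a few sentences of SAP text and an extra row in four table shells. The downside is a second denominator to explain, and the stated rates may be slightly higher.

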9.3.1. Solicited Events and Symptoms

Systemic and mucosal (local) solicited adverse events will be collected from the time of study vaccination through 14 days after study vaccination. Systemic events include: fever, chills, fatigue, malaise, myalgia, arthralgia, headache, and hypersensitivity. Mucosal events include: runny nose, stuffy nose/congestion, nasal pain/irritation, epistaxis, sneezing, sinus pressure/pain, sore throat, cough, and shortness of breath. Solicited AEs will be summarized by severity for each day after the study vaccination (Days 1-14 post study vaccination) and as the maximum severity over all 15 days ([Table 38](#), [Table 40](#), [Table 41](#), [Table 42](#), [Table 43](#), [Table 44](#), [Table 45](#), [Table 46](#), [Table 47](#), [Table 48](#), [Table 49](#), [Figure 9](#), [Figure 10](#), [Figure 11](#), and [Figure 12](#).) Severity will be graded on a scale of 0 (absent), 1 (mild), 2 (moderate) and 3 (severe). Grading scales for mucosal and systemic solicited adverse events are presented in [Table 6](#), [Table 7](#), and [Table 8](#), respectively. Additionally, solicited AEs will be analyzed by taking the most severe response over the follow-up period, dichotomizing into a binary variable (none versus mild, moderate, or severe) and using standard techniques, such as exact confidence intervals, to summarize the proportion of subjects reporting each symptom, any local symptom, and any systemic symptom ([Table 39](#).) Summaries of solicited AEs will be presented by treatment arm ([Table 36](#).) The proportion of subjects reporting symptoms will be compared between treatment arms using Chi-square or Fisher's exact test ([Table 37](#).) Solicited adverse events by subject will be presented in [Listing 10](#) and [Listing 11](#).

9.3.2. Unsolicited Adverse Events

Unsolicited AEs will be coded by Medical Dictionary for Regulatory Activities (MedDRA) for preferred term and system organ class (SOC). Unsolicited SAEs will be collected from the time of study vaccination through approximately 6 months after study vaccination and reported by detailed listings showing the event description, MedDRA preferred term and SOC, relevant dates (study vaccinations and AEs), severity, relatedness, and outcome for each event ([Listing 12](#)). Non-serious unsolicited AEs will be collected from time of study vaccination through approximately 28 days after study vaccination and summarized as number and percentage of subjects reporting at least one event in each MedDRA preferred term and SOC, cross tabulated by severity and relationship to study product ([Table 51](#), [Table 52](#), [Table 53](#), [Table 54](#), [Table 55](#), and [Figure 13](#)) and listed in [Table 56](#). Additionally, the proportion of subjects and exact 95% confidence intervals of AEs in aggregate and by MedDRA categories will be computed ([Table 50](#).)

9.4. Deaths, Serious Adverse Events and other Significant Adverse Events

The following listings will be presented including Subject ID, Adverse Event Description, Number of Days Post Dose (Duration), Reason Reported as an SAE, Relationship to Treatment, Alternate Etiology if not Related, and Outcome:

- Deaths and Serious Adverse Events ([Table 56](#))
- Non-Serious Adverse Events ([Table 57](#))
- New Onset Chronic Medical Conditions and Adverse Events of Special Interest ([Table 58](#))

9.5. Pregnancies

Safety population who become pregnant during the study, every attempt will be made to follow these subjects to completion of pregnancy to document the outcome, including information regarding any complications with pregnancy and/or delivery. A listing of pregnancies and outcomes will be presented ([Listing 19](#), [Listing 20](#), [Listing 21](#), [Listing 22](#), and [Listing 23](#).)

9.6. Clinical Laboratory Evaluations

Clinical safety laboratory adverse events will be collected at the time of study vaccination through approximately 7 days after study vaccination (Day 8). Any clinical laboratory parameter that is abnormal at Day 8 will be repeated at the next study visit (or sooner if medically indicated) and followed until normal or stabilization. Parameters to be evaluated include white blood cell count, platelet count, hemoglobin concentration, alanine aminotransferase (ALT), and creatinine. Grading scales for safety laboratory parameters are presented in [Table 9](#).

The number and percentage of subjects with at least one clinical safety laboratory abnormality through Day 8 is presented in the overall summary of adverse events ([Table 34](#).)

The distribution of chemistry results by severity, time point, and treatment group will be presented in [Table 61](#), [Table 62](#), [Table 63](#), [Table 64](#), [Table 65](#), [Table 66](#), and [Figure 14](#). The distribution of hematology results by severity, time point, and treatment group will be presented in [Table 69](#), [Table 70](#), [Table 71](#), [Table 72](#), [Table 73](#), [Table 74](#), [Table 75](#), [Table 76](#), and [Figure 15](#). Descriptive statistics including mean, standard deviation, median, minimum and maximum values by time point, for each laboratory parameter, will be summarized in [Table 67](#) and [Table 68](#) (chemistry) and [Table 77](#), [Table 78](#), and [Table 79](#) (hematology). Changes in laboratory values will be presented in [Figure 16](#), [Figure 17](#), [Figure 18](#), [Figure 19](#), and [Figure 20](#).

Subject visits with abnormal laboratory results, Grade 1 severity or higher, will be presented in [Table 59](#) and [Table 60](#).

[Listing 14](#) and [Listing 15](#) will provide complete listings of individual clinical laboratory results with applicable reference ranges.

9.7. Vital Signs and Physical Evaluations

Vital sign measurements will include systolic blood pressure, diastolic blood pressure, oral temperature, and pulse. Vital signs will be assessed at screening and at baseline prior to study vaccination. As abnormal vital signs are not expected, these will be listed by subject and time point ([Listing 16](#).)

Full Physical Examinations will be performed at screening. Limited physical examinations focused on the nasopharynx, oropharynx, and lungs will be performed at Day 1, Day 8, and Day 15. If indicated based on review of interim medical history, a targeted physical examination will be performed at each in-clinic visit. A listing of physical exam findings will be presented ([Listing 17](#).)

9.8. Concomitant Medications

Concomitant medications will be coded to the Anatomical Therapeutic Classification using the WHO Drug Dictionary. The use of prior and concomitant medications taken during the study will be recorded on the CRFs. A by-subject listing of concomitant medication use will be presented in [Listing 18](#). The use of concomitant medications during the study will be summarized by ATC1, ATC2 code and treatment group for the Safety population ([Table 80](#).)

9.9. Other Safety Measures

Not applicable.

